4. STUDY DESIGN

4.1. Study Description

A pilot pragmatic trial involving 2 multi-component PWM programs participating in POWER (Pediatric Obesity Weight Evaluation Registry) will be conducted to determine the feasibility of implementing a “bundle of program enhancements” (BPE) and its acceptability to 40 adolescents (ages 12-18) with severe obesity.

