6. STUDY PROCEDURES

Screening Visit— Adolescents and their parents/guardians who appear to qualify for the study based on the telephone interview will be scheduled to attend a screening visit. At the screening visit, height and weight measurements for the adolescent will be obtained by a qualified member of the study staff, using a standardized protocol and demographic information (date of birth, sex, race, ethnicity, and type of health insurance coverage) will be obtained and recorded. Adolescents and their parents/guardians who meet all inclusion/exclusion criteria, and express interest in participating in the study, will engage with a qualified member of the study staff who will review the consent/assent with the participant and their parent/guardian to ensure information presented is understood prior to obtaining the appropriate signatures for the IRB-approved informed consent/assent form. At the screening visit, participants and their parents/guardians who have met all criteria and informed consent/assent was obtained, will be enrolled in the study. Enrolled subjects at the screening visit will then be randomly assigned to either the *Intervention* or *Control* group, using a 2 *Intervention*:1 *Control* randomization ratio. At the end of the screening visit, all participants will be given a reminder card about their scheduled initial medical assessment visit with the PWM program. The week prior to this clinic visit, they will also receive a reminder call. This initial medical visit with the PWM program will serve as the baseline assessment visit for the study.

Group Assignment – Subjects will be randomized to either the Intervention or Control group using a 2 *Intervention*:1 *Control* randomization ratio. The randomization plan will be stratified by study site such that the 2:1 randomization ratio will be obtained within each study site. In addition, randomization will be stratified by baseline obesity status (Class 2, Class 3) to ensure the appropriate balance of obesity classes within each treatment group. A statistician independent from the study team will provide the

randomization plan so that the study team is blinded to the group assignment for each newly enrolled patient until that patient is randomized.

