Aim 3: The rate of participation in on-site scheduled visits (i.e. clinic visits, group sessions) will be calculated for each patient in both the intervention group and the control group as the percentage of all scheduled visits during the 6-month period that was attended by the patient. These percentages will be compared between groups using the mixed effects model with treatment as a factor and site as a random effect. Additional covariates in the model may include baseline weight status as measured by percent of the 95th percentile, sex, race, ethnicity, socioeconomic status, and distance from clinic site. To the extent possible, interactions of covariates with treatment group will be examined and discussed if significant at $p<0.10$ level of significance.

Transformations will be used (e.g. arcsin square root, log, rank) if needed to satisfy the assumptions of the model. The percentage of patients that complete the 6-month program will be analyzed using the same approach discussed above. In addition to doing hypothesis testing, treatment differences (unadjusted and also adjusted for covariates) and 95% confidence intervals will be presented.

Aim 4: Health outcomes measured by weight status, body composition, and blood pressure will be compared between the intervention and control groups using the repeated measures mixed effects analysis with center as a random effect. The outcome metric for weight status in the proposed study will be the change in percent of the 95th percentile for BMI (based on age and sex).

For each outcome, change from baseline will be calculated and included as the dependent variable. Terms in the model will include treatment, month (i.e. 3, 6 month) and the interaction of treatment by month. If the interaction is not significant at the two-sided $p<0.10$ level, it will be removed from the model. Appropriate contrasts will be used to compare the treatment groups at 3 months and at 6 months. Covariates in the model may be the same as those listed in Aim 3. The respective baseline measure may also be included as a covariate in the model for each health outcome. Laboratory measures will be measured at baseline and at 6 months of treatment. The mixed effects model using change in laboratory measure as the dependent variable and treatment as independent variable and center as random effect will be used. Covariates may include those listed for Aim 3 and the respective baseline laboratory measure.

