8.2. Sample Size Calculation

Sixty subjects will be enrolled in this study across the two sites with 40 subjects randomized to the Intervention group and 20 subjects to the Control group. This is a pilot study and therefore confirmatory hypothesis testing will not be done. Therefore, formal power calculations were not done. Table 2 shows the width of the two-sided 95% confidence intervals for various percentages and sample sizes. Table 3 provides the treatment effects that are detectable with various sample sizes.

Table 2. Sample Size and 95% Confidence Intervals for an Observed Percentage for Study Aims 1 and 2

Observed Percentage	Sample Size			
	N=40		N=30	
	Lower 95% CL	Upper 95% CL	Lower 95% CL	Upper 95% CL
50%	35%	65%	33%	67%
65%	49%	78%	47%	79%
80%	65%	89%	63%	90%
95%	83%	99%	81%	99%

Table 3. Sample Size and Treatment Effect

Sample size Intervention/Control	Detectable Treatment Effect					
	80% Power		70% Power		50% Power	
	p<0.05	p<0.10	p<0.05	p<0.10	p<0.05	p<0.10
40/20	0.8	0.7	0.7	0.6	0.5	0.5
30/15	0.9	0.8	0.8	0.7	0.6	0.5

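### Aims 3 and 4 treat site as random with only two sites; fitting site and obesity class as fixed factors would match the randomisation at almost no cost (minor)

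*Combined protocol and SAP*

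**What the plan says.** Section 4.1 describes "A pilot pragmatic trial involving 2 multi-component PWM programs", and section 8.2 states "Sixty subjects will be enrolled in this study across the two sites"; the planned split is 40 intervention to 20 control. Under Group Assignment in section 6, "The randomization plan will be stratified by study site such that the 2:1 randomization ratio will be obtained within each study site"; obesity class (Class 2 or 3) is the second stratification factor.

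In section 8.1, attendance at scheduled visits (Aim 3) is compared "using the mixed effects model with treatment as a factor and site as a random effect". Six-month completion follows the same approach. Weight status, body composition and blood pressure (Aim 4) use a "repeated measures mixed effects analysis with center as a random effect", and the laboratory measures use a mixed model with centre random.

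No model has a fixed site term. No fallback is given for a zero site variance, and no degrees-of-freedom method is named. The covariate list is optional. It contains baseline weight status as a continuous measure, but neither site nor obesity class.

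**The concern.** A random site effect needs a between-site variance, and two sites supply a single contrast from which to estimate it. When the observed site difference is no larger than sampling noise, the REML estimate is zero and the fitted model contains no site term, although site was a randomisation factor. Because this happens outcome by outcome, the set of secondary results may mix site-adjusted and unadjusted comparisons without anyone having chosen that.

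Site could matter here. Group sessions are held only where offered, the follow-up encounters are tailored to each site (Rationale for the Study), and participation and retention are themselves Aim 3 outcomes. Attrition is a known problem: Preliminary Studies reports that 61% of registry adolescents had at least one follow-up visit. If loss differs by site and arm, the arms no longer have the same site mix, and a zero or shrunken site effect lets part of the site difference into the treatment estimate. The pilot's treatment-effect estimates are meant to inform the design of a larger trial.

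**Working it through.** **Inputs.** From the documents: 2 sites, 60 participants, 40 against 20, 2:1 within site. Assumed, because the documents do not give them: 30 per site, the size of any true site difference (in SD units), the intraclass correlation (ICC), and the pattern of loss.

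**1. The plan's own figure.** Table 3 gives a detectable effect of 0.8 for 40/20 at 80% power and p<0.05. The table states no unit; SD units are assumed. The normal approximation is (1.960 + 0.842) × √(1/40 + 1/20) = 2.802 × 0.274 = 0.767. The noncentral t gives 0.780, which rounds to 0.8. All 12 entries are reproduced this way. Table 3 is thus consistent with a plain two-sample comparison with a standard error of about 0.27 SD. The documents give no figure for site variance.

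**2. How often the site variance is zero.** With 30 per site and observed site difference D, the estimate is max(0, D²/2 − s²/30). It is zero when |D| < s√(2/30) = 0.258s, that is, when the site F statistic on 1 and 57 df is below 1. For a true difference δ the noncentrality is δ² × 30 × 30/60 = 15δ².

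| True site difference (SD) | 15δ² | P(estimate = 0) |
|---|---|---|
| 0 | 0 | 68% |
| 0.2 | 0.60 | 55% |
| 0.3 | 1.35 | 42% |
| 0.5 | 3.75 | 17% |
| 0.8 | 9.60 | 2% |

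In terms of ICC, P = P(F(1,57) < 1/(1 + 30·ICC/(1 − ICC))): 68% at 0, 57% at 0.02, 46% at 0.05, 37% at 0.10 and 27% at 0.20. Splits of 37/23 or 40/20 change the figures in the table by at most about 3 points and those by ICC by at most 2. REML simulation (800 trials per scenario, 30/30 and 37/23) gave 67% to 70% at ICC 0, 53% to 60% at 0.02, 44% to 49% at 0.05 and 35% to 37% at 0.10.

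**3. Outcomes affected.** Participation and completion (2), weight status (1), body composition (3), blood pressure (2) and laboratory measures (5): 13 in all.

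**4. Effect with complete data.** In the same simulations, random and fixed site gave identical treatment estimates with 20:10 at each site. They differed by at most 0.0084 SD with 25:12 and 15:8. Mean standard errors differed by less than 0.5%. Power at 0.8 SD was 80.3% to 85.4% with random site and 80.1% to 85.4% with fixed site. Type I error was 3.6% to 5.8% against 3.5% to 5.5% (Monte Carlo SE about 0.8 points).

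**5. Effect with unbalanced loss.** If site dropped out entirely, the bias would be (share of the intervention arm at site A − share of the control arm at site A) × δ.

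- Moderate: 18/8 and 14/9 retained (intervention/control). The shares differ by 18/32 − 8/17 = 0.092, so at δ = 0.5 the bias would be 0.046 SD.
- Extreme: 19/5 and 11/9 retained. The shares differ by 19/30 − 5/14 = 0.276, so at δ = 0.5 the bias would be 0.138 SD.

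The random-site model drops site only sometimes and otherwise shrinks it, so the average bias is smaller. In REML simulations it was at most about 0.014 SD in the moderate case and peaked at about 0.044 SD in the extreme case, against a root mean squared error (RMSE) of about 0.33 SD. Three other patterns (18:6 and 12:9; 19:5 and 12:9; 16:5 and 10:8), with site differences of 0.2 to 0.5 SD, gave average shifts of about 0.02 to 0.04 SD and up to about 0.1 SD in single trials. Fixed site was unbiased within Monte Carlo error.

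All simulations used one continuous outcome at one time point. The repeated-measures and binary completion models have the same two clusters but were not simulated.

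**The case against.** The strongest reply is that nothing important changes. Allocation is 2:1 within each site, so treatment is almost orthogonal to site, and with balanced data the estimate, standard error, power and type I error are essentially the same either way. The problem also limits itself: the variance is set to zero only when the observed site difference is small. Even under the extreme loss pattern the bias is about one eighth of the estimate's standard error (0.044/0.33), type I error stays near nominal (5.0% to 5.7% random, 4.2% to 5.4% fixed), and for site differences up to 0.3 SD the random-site RMSE is equal or slightly lower. Only secondary aims are affected, and section 8.2 disclaims confirmatory testing.

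All of this stands, and it sets the weight of the point. It does not remove the point. Section 8.1 still tests these comparisons at the two-sided 5% level and reports adjusted differences with confidence intervals, so whether site is in the model should be settled beforehand and not by each outcome's data.

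A reader might infer more than the documents support:

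- That the variance cannot be estimated. It can, but very imprecisely.
- That the models will fail to converge. No such failure was shown, and a boundary fit still yields a usable treatment estimate.
- That the plan claims inference to a population of programmes. It makes no such claim from these models, although Preliminary Studies calls the two sites representative of the registry.
- That a fixed site term alone would honour the stratification. It would not, because obesity class was also a stratification factor.

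**Conclusion.** The point holds as a minor matter of model specification. With two sites, the random effect makes site adjustment depend on a variance with one degree of freedom. That variance is estimated as zero about 68% of the time with no site difference and 17% of the time at 0.5 SD, assuming 30 per site, but only about 2% at 0.8 SD. The effect on the treatment comparison is negligible with balanced data. Under assumed loss that differs by site and arm it is a bias of about 0.01 to 0.04 SD on average. The documents give no loss by site and arm, so that range illustrates and does not predict.

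A reader might conclude that the planned comparisons are invalid or lose power. The calculations do not support that: neither power loss nor material type I error inflation was found. The change tidies a sound analysis and does not rescue a failed one. The effect of leaving out obesity class was not calculated; that part rests on matching the analysis to the randomisation.

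**What to change.** In section 8.1, for all Aim 3 and Aim 4 models:

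- Fit site as a fixed two-level factor in place of the random site or centre effect.
- Include obesity class (Class 2 or 3), the other stratification factor, as a fixed effect.
- Keep random or repeated-measures terms only for the participant, in the models with 3- and 6-month data. Participation, completion and the laboratory changes have one value per participant and need none.
- State that inference from these models is to the two participating programmes.

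The cost is a change of wording and about two residual degrees of freedom: with one value per participant, from 60 − 2 = 58 with treatment alone to 60 − 4 = 56 with site and class added, before optional covariates. In the simulations the fixed site term raised the mean standard error by less than 0.5%. No wider claim is lost, because two sites could not support one.

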Hypothesis 3.1. Participants in the *Intervention* group will have a greater rate of participation in the standard-of-care PWM program as measured by percent of scheduled clinic visits and group sessions (if offered) attended over the 6-month treatment period, compared to those assigned to the *Control* group (N=20)

Hypothesis 3.2. Participants in the *Intervention* group will have a greater retention rate (percent of participants that complete the 6-month treatment period) than those in the *Control* group.

Secondary Aim 4 Test whether the *Intervention* group has better health outcomes when compared to the *Control* group after the 6-month treatment period. Health outcomes to be measured at baseline, 3-month, and 6-month assessment visits will include: 1) Weight status (BMI metric: percent of the 95th percentile); 2) Body composition (% body fat, skeletal muscle mass; fat-free mass); and 3) Blood pressure. Laboratory measures (HbA1c, ALT, non-HDL, TG, fasting glucose) will be obtained at baseline and 6-months.

Hypothesis 4. The *Intervention* group will have better health outcomes than the *Control* group.

Expected outcomes and impact: If the results of this pilot pragmatic study show that the BPE is feasible, acceptable and potentially effective, then we will have the information needed to design a fully-powered multi-site clinical trial to evaluate the efficacy of the BPE as an enhancement for existing multi-component PWM programs. If it is found that the BPE is efficacious, this evidence-based approach can then be widely implemented in order to improve the treatment of adolescents with severe obesity.

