2	% of scheduled FIEs between clinic visits completed (Intervention Group only)	
	% of subjects that achieve 26 hours of contact time (Intervention Group only)	
3	% of scheduled standard-of-care clinic visits attended (Intervention and Control Groups)	Clinical Assessment Visits (Intervention and Control Groups) Baseline, 3-, and 6-month assessments Tracking form for anthropometric and body composition measurements, and blood pressure.
	% of subjects that complete 6-month treatment period (Intervention and Control Groups)	
4	Anthropometric measurements (height, weight) BMI outcome metric: % of the 95 th percentile for BMI	
	Body composition (% body fat, skeletal muscle mass, fat-free mass)	
	Blood pressure (systolic, diastolic)	
4	Laboratory values* (fasting) (HbA1c, ALT, glucose, non-HDL cholesterol, and TG)	Clinical Assessment Visits (Intervention and Control Groups) Baseline and 6-month assessments Tracking form for laboratory measures

Three-month and Six-month Assessments: Participants will be assessed following the same procedures as for the baseline assessment, with measurement of height, weight, body composition, and blood pressure. If the participant is at Tanner stage I, II, or III at the baseline visit, Tanner staging will be assessed again at the six-month visit. Fasting blood work will be obtained at the 6-month assessment visits. The results of all clinical measurements and laboratory values will be recorded on the study's source document, specific for each subject (Table 1). Completion of the 3-month and 6-month reassessment clinic visits can occur 2-weeks prior or 4 weeks after the 3-month and 6-month time points.

Table 1 Schedule of Procedures

Elapsed Time	Screening Visit	Baseline Medical Visit	#Month 3 Medical Assessment	#Month 6 Medical Assessment	Telehealth/Phone/Email remote encounters between visits	Other clinical in-person encounters
Randomization	X					
Height and Weight	X	X	X	X		X
Body Composition (%body fat, skeletal muscle mass, fat-free mass)		X	X	X		X
Blood Pressure		X	X	X		X
Demographics	X					
Program orientation session detailing site-specific description of pediatric weight management program	X*					
Mental Health Assessments	X*					
Readiness to change assessment	X*					
Schedule Follow-up Interactive Encounters		X*	X*		X*	X*
Review Medical History		X	X	X		X
Physical Exam		X	X	X		X
Blood for serum chemistry		X		X		
Assess for adverse events		X	X	X	X	X
Medication Review		X	X	X		X

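### Aim 4 models raw change in fat-free and skeletal muscle mass in 12-18-year-olds without baseline age as a covariate, which gives away some precision

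*Combined protocol and SAP*

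**What the plan says.** Section 3 (Secondary Aim 4) lists the health outcomes, among them "Body composition (% body fat, skeletal muscle mass; fat-free mass". Section 8.1 (Aim 4) sets the dependent variable: "For each outcome, change from baseline will be calculated and included as the dependent variable". The model has treatment, month (3 and 6), their interaction and a random centre effect.

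Only weight status is referenced to growth, as "change in percent of the 95th percentile for BMI (based on age and sex". No age, height or maturity reference is stated for the body-composition measures.

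The covariates are optional and borrowed: "Covariates in the model may be the same as those listed in Aim 3". The Aim 3 list, written for attendance at visits, is baseline percent of the 95th percentile together with "sex, race, ethnicity, socioeconomic status, and distance from clinic site". Section 8.1 also allows the outcome's own baseline value: "The respective baseline measure may also be included as a covariate in the model for each health outcome". Age and Tanner stage are not named as covariates anywhere in Section 8.

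On the data available, the Screening Visit text in Section 6 records "demographic information (date of birth, sex, race, ethnicity, and type of health insurance coverage". For participants at stage I to III at baseline, Section 6 says "Tanner staging will be assessed again at the six-month visit". Neither the Baseline Assessment text nor the Schedule of Procedures lists Tanner staging. Randomisation (Section 6, Group Assignment) is 2:1, stratified by site and by obesity class (Class 2, Class 3).

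**The concern.** Between 12 and 18 years, six-month change in lean mass depends partly on how much a participant is still growing, and age is the simplest marker of that. The plan deals with growth for weight status by using an age- and sex-referenced metric, but has no counterpart for fat-free or skeletal muscle mass. The covariates it offers for those outcomes were chosen to explain attendance.

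Omitting age leaves growth-related variation in the residual. Both arms then carry avoidable noise, and any chance difference in age between 40 and 20 participants stays in the estimate. The Preliminary Studies text says the pilot should supply treatment-effect estimates for a fully powered trial, so the precision of those estimates has some value. The open list also leaves the choice of covariates until after the data are seen.

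**Working it through.** **Inputs from the documents.** 40 Intervention and 20 Control (Section 8.2); two-sided 5% level (Section 8.1); detectable effect 0.8 at 80% power and p<0.05 (Section 8.2, Table 3). The table does not label its units; they are read here as standard deviations.

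**Input assumed.** R², the share of change-score variance that age explains beyond sex and the outcome's baseline value. The documents give no figure. The range used is 0.05 to 0.30.

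1. *Reproduce the plan's figure.* Detectable difference = (1.960 + 0.842) × √(1/40 + 1/20) = 2.802 × 0.274 = 0.767 SD. The t-based version gives 0.780. Both round to the stated 0.8, so Table 3 is an unadjusted two-group calculation.

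2. *Effect of adjusting.* The standard error is multiplied by √(1 − R²). The detectable effect is in units of the SD of change before age is added.

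| R² (assumed) | SE factor | SE cut | Detectable effect, 80% power | Power at 0.5 SD | Equivalent N = 60/(1 − R²) |
|---|---|---|---|---|---|
| 0 | 1.000 | 0% | 0.77 | 45% | 60 |
| 0.05 | 0.975 | 2.5% | 0.75 | 47% | 63 |
| 0.10 | 0.949 | 5.1% | 0.73 | 49% | 67 |
| 0.20 | 0.894 | 10.6% | 0.69 | 53% | 75 |
| 0.30 | 0.837 | 16.3% | 0.64 | 59% | 86 |

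3. *Cost of the extra term.* Estimating one covariate slope inflates the expected variance of the arm difference by about 1 + 1/(N − 4) = 1 + 1/56 = 1.018, or 0.9% in the standard error. Net of this, R² = 0.05 gives √(0.95 × 1.018) = 0.983 and R² = 0.30 gives √(0.70 × 1.018) = 0.844. The net cut is therefore about 2% to 16%. The term breaks even when (1 − R²) × 57/56 = 1, that is at R² = 1/57, about 2%.

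4. *Is chance imbalance an additional harm?* If the SD of age is 1.5 to 2.0 years (assumed; a uniform spread over 12 to 18 gives 1.7), the SE of the arm difference in mean age is 0.274 × 1.5 = 0.41 to 0.274 × 2.0 = 0.55 years. A gap above half a year then has a probability of 22% to 36%. Such gaps move the outcome difference with an SD of √R² × 0.274, which is 0.06 (R² = 0.05) to 0.15 (R² = 0.30) outcome SD. This is already part of the unadjusted variance: R² × 0.075 + (1 − R²) × 0.075 = 0.075, where 0.075 = 1/40 + 1/20. At 1.96 SE the shift is 0.12 to 0.29 SD, inside the unadjusted 95% half-width of 1.96 × 0.274 = 0.54 SD. Imbalance and residual noise are one loss, and the interval already covers it.

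**The case against.** The strongest reply is that little is at stake. Aim 4 is secondary, Section 8.2 disclaims confirmatory testing, Aims 1 and 2 are untouched, and the weight outcome is already referenced to age and sex. Nothing in the documents indicates that lean mass would drive the design of the next trial. The covariate wording is permissive, so age is not excluded, and sex and the baseline value, if used, would absorb part of the maturity effect. All of this stands. It limits the size of the point but does not remove it: the permitted covariates are optional, and age is available at almost no cost.

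A reader might infer more than the documents support:

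- *That age and puberty are unbalanced by design, or that the comparison is biased.* They are not stratified, but randomisation balances them in expectation, and growth common to both arms cancels in the contrast.
- *That the precision loss could be close to 30%.* Suppose 40% of participants are growing and gain 1 to 3 kg more lean mass, with a within-group SD of 2 to 1.5 kg. Growth's share of variance is then 0.24/4.24 = 5.7% to 2.16/4.41 = 49%, and the SE cut is 3% to 29%. None of these inputs is in the documents, the ends pair extreme values, and the figure ignores what sex and the baseline value already explain.
- *That blood pressure suffers equally.* The documents give nothing to size it, and the effect over six months may be small.
- *That baseline Tanner stage is on file and simply unused.* The six-month rule implies a baseline stage, but no baseline procedure lists one.

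**Conclusion.** The point holds as a modest precision improvement for fat-free mass and skeletal muscle mass. The plan leaves out a relevant baseline variable that it collects, and offers covariates chosen for another purpose. The unadjusted estimate and its confidence interval remain valid. On an assumed R² of 5% to 30% beyond sex and the baseline value, adjustment shortens the standard error by about 3% to 16%, or about 2% to 16% after paying for the extra term. If age explained less than about 2%, there would be no gain. The size rests wholly on that assumption. The documents do not support a claim of bias, of a design fault in the randomisation, or of a material effect on blood pressure.

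**What to change.** In Section 8.1, Aim 4, pre-specify these covariates for the fat-free mass and skeletal muscle mass models: age at baseline, sex, the outcome's own baseline value, and obesity class (or baseline percent of the 95th percentile). The last should stay because it corresponds to a stratification factor; discarding the whole carried-over list would lose it.

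Add baseline Tanner stage only if the sponsor confirms that it is recorded for all participants. Age may also be added to the blood pressure model, with little gain expected.

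Indexing lean mass to height squared, or reporting the lean-mass outcomes only descriptively, are matters of preference and are not needed to resolve this point.

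The cost is a wording change plus one or two degrees of freedom in a 60-participant model. Age needs no new data, since date of birth is already collected.

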8. DATA ANALYSIS

8.1. Study Endpoints

Demographic and clinical characteristics will be summarized overall and within each center using frequency and percent for categorical data and median and interquartile range for the continuous measurements. For each aim below, the two-sided 95% confidence intervals will be calculated using the Score Confidence Interval.³⁴ All comparisons between the intervention and control groups will be tested at the two-sided, 5% level of significance.

Aim 1: For patients in the intervention group only, percentages and two-sided 95% confidence intervals will be presented for the each of the components of the “Bundle of Program enhancements (BPE)”: a) percent of participants attending the program orientation; b) percent of participants completing each of the mental health questionnaires; 3) percent of participants completing the “readiness to change” clinical assessment; 4) percentage of participants that complete scheduling of interactive encounters (FIE) between clinic visits for 1st month of treatment; and 5) Percent of participants that complete scheduling of FIE between clinical visits for each of months 2-6 of treatment. Each confidence interval will be examined to determine if the hypothesized value of 80% is contained within the interval.

Aim 2: For patients in the intervention group only, the percentages and two-sided 95% confidence intervals will be calculated for the intervention group only for the percent of patients that complete at least 26 contact hours during the 6-month treatment period. The confidence interval will be examined to determine if the hypothesized value of 70% is contained within the interval. In addition, the mean and 95% confidence interval will be presented for the percent of FIE completed by each patient and also for the total number of contact hours completed by each patient. These measures will also be provided for the subset of patients in the intervention group that are identified with mental health problems and descriptively compared to the subset of patients in the intervention group without mental health problems.

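### Obesity class stratifies the randomisation but is required in no Aim 3 or Aim 4 model, and no lead model is named, so between-arm precision is understated if class is prognostic

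*Combined protocol and SAP*

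**What the plan says.** - **Design.** Section 6 (Group Assignment) stratifies the 2:1 randomisation by site and then adds: "In addition, randomization will be stratified by baseline obesity status (Class 2, Class 3". Section 8.2 gives "40 subjects randomized to the Intervention group and 20 subjects to the Control group".
- **Test level.** Section 8.1: "All comparisons between the intervention and control groups will be tested at the two-sided, 5% level of significance".
- **Aim 3.** Attendance percentages are compared in a mixed model with treatment and a random site effect. Beyond that, "Additional covariates in the model may include baseline weight status as measured by percent of the 95th percentile, sex, race, ethnicity, socioeconomic status"; how far the family lives from the clinic is the sixth candidate. Completion of the program is analysed in the same way. The Aim 3 text ends: "In addition to doing hypothesis testing, treatment differences (unadjusted and also adjusted for covariates) and 95% confidence intervals will be presented".
- **Aim 4.** The repeated-measures model has treatment, month, treatment by month (dropped if not significant at 0.10) and a random center effect. "Covariates in the model may be the same as those listed in Aim 3". The outcome's own baseline value is also optional. The Aim 3 sentence on unadjusted and adjusted differences is not repeated here.
- **Status of testing.** Section 8.2: "This is a pilot study and therefore confirmatory hypothesis testing will not be done". On power, the same section states: "Therefore, formal power calculations were not done".

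**The concern.** The randomisation has two stratification factors and the analysis keeps one of them. Stratifying by class forces the arms to be balanced on it. If class predicts outcome, the treatment difference then varies less from trial to trial than a model without class assumes. That model leaves the between-class variation in its residual, so it reports a standard error that is too large, an interval that is too wide and a test that rejects less often than stated. The trial loses the precision that its design has already secured.

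The optional covariate, baseline percent of the 95th percentile, does not close the gap. Nothing requires it. It is also not the stratum as randomised: Section 6 places randomisation at the screening visit and the baseline assessment at the later initial medical visit.

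The companion gap is the lead result. Six covariates may or may not enter, Aim 3 reports differences with and without them, and nothing says which estimate answers Hypotheses 3.1, 3.2 or 4. Section 3 uses this pilot to judge whether the enhancements are potentially effective, and Section 2 says that it will supply treatment-effect estimates for a full trial. A planner needs to know which estimate and interval to carry forward.

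**Working it through.** **1. The plan's own figure.** Table 3 gives a detectable effect of 0.8 for 40/20 at 80% power and two-sided 0.05. By the normal formula, (1.960 + 0.842) × √(1/40 + 1/20) = 2.802 × 0.2739 = 0.767. The noncentral t version gives 0.780. Both round to 0.8, so the table is reproduced. It takes no credit for the stratification.

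**2. Standard error without class.** From the documents: 60 participants, 2:1, stratified by site and class. Assumed: four equal strata of 15, each split exactly 10:5; a continuous outcome with total variance 1; class explains a share R². The documents give no figure for R², so a range is shown.

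- Class is balanced across arms, so it cancels from the treatment difference. True variance = (1 − R²)(1/40 + 1/20).
- With treatment and site only, the class sum of squares, 60R², stays in the residual, which has 60 − 3 = 57 degrees of freedom. Expected residual variance = (1 − R²) + 60R²/57.
- Reported SE ÷ true SE = √{1 + 60R² / [57(1 − R²)]}.

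**3. Rejection rate under no effect.** The 5% critical value on 57 df is 2.002. Reporting an SE that is too large has nearly the effect of multiplying this threshold by the SE ratio.

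| R² for class | SE ratio | Effective threshold | Rejection, t on 57 df | Rejection, simulated (20,000 trials) |
|---|---|---|---|---|
| 0.05 | √(1 + 3/54.15) = 1.027 | 2.057 | 4.4% | 4.3% |
| 0.10 | √(1 + 6/51.3) = 1.057 | 2.116 | 3.9% | 3.8% |
| 0.20 | √(1 + 12/45.6) = 1.124 | 2.251 | 2.8% | 2.9% |

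A second simulation of the same design gave about 4.1% and 2.8% for R² of 0.10 and 0.20. A third, with permuted blocks of three and class explaining about 9%, 23% or 33%, gave 4.0%, 2.4% and 1.8%. With class in the model, rejection was 4.9% to 5.2% wherever class was prognostic.

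**4. What this means for detectable effect** (80% power, normal approximation, in units of the total SD):

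- R² = 0.10. Class omitted: 0.2739 × (1.960 × √1.0053 + 0.842 × √0.9) = 0.757. Class included: 0.767 × √0.9 = 0.728.
- R² = 0.20. Class omitted: 0.2739 × (1.960 × √1.0105 + 0.842 × √0.8) = 0.746. Class included: 0.767 × √0.8 = 0.686.

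So including class lowers the detectable effect by about 4% or 8%.

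**5. The unnamed lead result.** Six optional covariates allow 2⁶ = 64 main-effect sets. Two null simulations (40 vs 20, site in every model) assumed different joint covariate strengths:

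| Rule | Joint R² 0 to 0.4 | Joint R² 0 / about 0.24 / about 0.54 |
|---|---|---|
| One model fixed in advance | about 5% | 4.1% to 5.0% |
| Unadjusted or full model, either significant | 6.5% to 8.1% | 6.3% / 7.1% / 7.3% |
| Best of all 64 sets (worst case) | 8.7% to 18.3% | 8.4% / 13.3% / 20.8% |

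Rows two and three apply only if the result that counts is picked after the results are seen.

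**The case against.** The case for leaving the text alone is a good one. Aims 3 and 4 are secondary, Section 8.2 disclaims confirmatory testing, and the primary aims rest on intervention-arm percentages that no covariate choice touches. Treatment plus site can be read as the base model, with covariates as supplements. Showing both unadjusted and adjusted differences is open reporting. Omitting a balanced stratum errs on the safe side. No section shows that class predicts attendance, retention or change scores, and at R² = 0.05 the loss is slight. The simulations use least squares on one continuous outcome with a fixed site effect, whereas completion is binary and most Aim 4 outcomes are repeated.

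Most of this limits the size of the point and does not remove it. Conservative tests are still miscalibrated, and in a trial this small wide intervals are a real cost. The pilot label does not help either: an estimate and interval for planning need a defined model even when no p-value is claimed.

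Two stronger readings should be resisted.

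- A reader might infer that the 5% error rate fails for Aims 3 and 4. The documents do not support that. Any single model set in advance holds 5% or less, and the plan contains no rule that the best of several results counts. Omitting class lowers the rejection rate; it does not inflate it.
- A reader might also infer that both unadjusted and adjusted differences are promised for Aim 4. That sentence stands under Aim 3 only; Aim 4 takes over just the optional covariate list.

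**Conclusion.** The point holds as one of design and analysis not matching. Obesity class is a randomisation factor and is required in no between-arm model. If it explains 5%, 10% or 20% of outcome variance, reported SEs are about 3%, 6% or 12% too large and a nominal 5% test rejects about 4.3%, 4% or 3%; including class restores about 5%. If class is not prognostic, nothing is lost either way. These figures assume equal strata, exact 2:1 allocation and a linear model for a continuous outcome. The size for the binary completion outcome and for the repeated-measures models was not computed.

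The missing lead model is a useful companion, mainly a gap in detail. It leaves 5% unassured only if the model is chosen after results are seen: about 6% to 8% for the two Aim 3 results, and more only in a worst-case search over all covariate sets. The consequence is for precision and for the estimates taken into the later trial. The feasibility and acceptability conclusions are unaffected.

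**What to change.** In Section 8.1:

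1. Require both randomisation factors, site and obesity class (Class 2/Class 3, as used at randomisation), in every Aim 3 and Aim 4 model, with the month terms for repeated outcomes as already planned.
2. Name this as the lead model, whose estimate and 95% confidence interval answer Hypotheses 3.1, 3.2 and 4.
3. Label the unadjusted difference, and any model adding the other listed covariates, as sensitivity analyses. That list includes baseline percent of the 95th percentile where it is not the outcome's own baseline value.

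The cost is a few sentences and one residual degree of freedom. No new data are needed, because class is already known when each participant is randomised.
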